6.2 Safety Assessments

6.2.1 Bleeding Assessment

Acute clinically overt bleeding is defined as new onset, visible bleeding or signs or symptoms suggestive of bleeding with confirmatory imaging techniques which can detect the presence of blood (e.g., US, CT, MRI).

The definition of major bleeding described below is adapted from the International Society on Thrombosis and Hemostasis (ISTH) definition

Major bleeding event is defined as a bleeding event that is:

- Acute clinically overt bleeding accompanied by one or more of the following:
 - A decrease in hemoglobin (Hgb) of 2 g/dL or more over a 24-hour period
 - A transfusion of 2 or more units of packed red blood cells
 - Bleeding that occurs in at least one of the following critical sites:
 - ◆ Intracranial
 - ◆ Intra-spinal
 - ◆ Intraocular (within the corpus of the eye; thus, a conjunctival bleed is not an intraocular bleed)

[name]

20

- ◆ Pericardial
- ◆ Intra-articular
- ◆ Intramuscular with compartment syndrome
- ◆ Retroperitoneal.

- Bleeding that is fatal.

Clinically relevant non-major bleeding event: The definition of clinical relevant non-major bleeding will be acute or sub-acute clinically overt bleeding that does not satisfy the criteria for major bleeding and that leads to either 1) hospital admission for bleeding or 2) physician guided medical or surgical treatment for bleeding or 3) a change in antithrombotic therapy.

Minor bleeding events: All acute clinically overt bleeding events not meeting the criteria for either major bleeding or clinically relevant non-major bleeding will be classified as minor bleeding.

Fatal bleeding event is defined as a bleeding event that the CEC determines is the primary cause of death or contributes directly to death. All acute clinically overt bleeding events will be adjudicated by the CEC as a major bleeding event, or clinically relevant non-major bleeding event. Minor bleeding events will not be adjudicated.

6.2.1.1 Treatment Guidelines for Bleeding/Suspected Bleeding

Subjects with bleeding or suspected bleeding will undergo confirmatory laboratory or other testing (e.g., US, CT, MRI) and a (S)AE CRF must be completed. The date and time of the onset of the bleeding event will be recorded on the CRF. Also, for subjects with bleeding, study drug may or may not be held at the discretion of the local physician and investigator. A risk / benefit determination should be made (as would be normally done with warfarin) weighing the subject's risk of further bleeding against the subject's risk of thromboembolism and benefit from continued anticoagulation. The bleeding should otherwise be managed according to local standard of care.

For subjects with clinically significant bleeding, the study drugs should generally be held. Bleeding should be managed according to local standard of care and may include measures such as:

- Local measures to stop the bleeding
- Volume resuscitation, and transfusion of blood products as appropriate
- Standard laboratory tests e.g. hemoglobin, hematocrit, PT/INR, aPTT, platelet count, etc. (recognizing that the anticoagulant effects of apixaban will not be reflected in standard coagulation tests)

6.2.2 Laboratory Assessments

Blood and urine samples will be obtained on selected visits (screening, quarterly visits, annual visits and at the end of treatment visit) for clinical laboratory evaluations. A central laboratory will perform the analysis and will provide reference ranges for these tests. The following laboratory tests are required for this study, and will be analyzed by a Central Laboratory:

Hematocrit, Hemoglobin, Red Blood Cell Count, MCV, White Blood Cell Count ,Lymphocytes, Platelet Count, Creatinine, ALP, ALT, AST, Direct Bilirubin and Total Bilirubin.

For the central laboratory assessments, materials and detailed instructions for specimen collection, processing, storage and shipment will be provided in special kits and will be described in a separate laboratory manual.

6.2.3 Pregnancy Tests

A pregnancy test to be conducted at the site:

- At screening
- On Day 1(if the screening pregnancy test is performed within 48 hours prior to first dosing of study medication, then the pregnancy test does not need to be repeated on Day 1)

[name]

21

- At all monthly visits
- At End of Treatment Visit

6.2.4 Creatinine Clearance

Based on the results of the enrollment visit clinical laboratory tests, the enrollment criterion for creatinine clearance will be estimated by the method of Cockcroft and Gault:

$$\text{Clcr (mL/min)} = [(140 - \text{age}) \times (\text{weight in kg}) (\times 0.85 \text{ for females})] / \text{serum creatinine (mg/dL)} \times 72$$

6.3 Efficacy Assessments

6.3.1 Primary Efficacy Assessment

The primary efficacy endpoint of the study will be the time to the first occurrence of confirmed stroke (hemorrhagic, ischemic or of unspecified type) or systemic embolism. Stroke and systemic embolism are defined below and will be adjudicated by the CEC.

Stroke

Diagnosis of stroke will require the abrupt onset of focal neurological symptoms lasting at least 24 hours. It is strongly recommended (but not required) that an imaging procedure such as a CT scan or MRI be performed. All strokes will be classified as definite ischemic, definite hemorrhagic or type uncertain. A vascular imaging procedure such as a carotid ultrasound is recommended whenever possible (but not required) for subclassification of ischemic strokes into cardioembolic, lacunar or large artery. The level of disability and stroke severity will be assessed at presentation and at the next two regularly scheduled follow-up visits using the modified Rankin score.

Systemic Embolism

Systemic embolism will be judged to occur where there is a clinical history consistent with an acute loss of blood flow to a peripheral artery (or arteries), which is supported by evidence of embolism from surgical specimens, autopsy, angiography, or other objective testing.

6.3.2 Secondary Efficacy Assessment

Secondary efficacy assessments will include assessments of combined efficacy and safety endpoints involving ischemic stroke, hemorrhagic stroke, stroke of unspecified type, systemic embolism, myocardial infarction, major bleeding and all cause death. The endpoints of death and non-fatal myocardial infarction (MI) are defined below and will be adjudicated by the CEC.

Death

Death will be defined as all-cause mortality. Deaths will be classified as either cardiovascular or non-cardiovascular. All deaths will be assumed to be cardiovascular in nature unless a non-cardiovascular cause can be clearly provided.

i) Cardiovascular

This category includes cardiac deaths (e.g., cardiogenic shock, arrhythmia/sudden death, cardiac rupture) and other cardiovascular deaths (stroke, pulmonary embolism, ruptured aortic aneurysm or dissection).

ii) Non-cardiovascular

This category includes all deaths due to a clearly documented non-cardiovascular cause, such as respiratory failure (excluding cardiogenic pulmonary edema), hemorrhage (other than intracranial), infections/sepsis, neoplasm, and trauma (including suicide and homicide).

[name]

22

Myocardial Infarction

The following criteria satisfies the diagnosis for an acute or evolving MI in an appropriate clinical context.

- elevation of CK-MB or Troponin T or I $\geq 2 \times$ the ULN, or
- if no CK-MB or troponin values are available, a total CK $\geq 2 \times$ ULN, or
- new, significant (≥ 0.04 s) Q waves in ≥ 2 contiguous leads.

UNIT 7 :Adverse Events

7.1 Definitions

An *Adverse Event (AE)* is defined as any new untoward medical occurrence or worsening of a pre-existing medical condition in a subject or clinical investigation subject administered an investigational (medicinal) product and that does not necessarily have a causal relationship with this treatment. An AE can therefore be any unfavorable and unintended sign (including an abnormal laboratory finding, for example), symptom, or disease temporally associated with the use of investigational product, whether or not considered related to the investigational product.

7.1.1 Serious Adverse Events

A *serious AE (SAE)* is any untoward medical occurrence that at any dose:

- results in death
 - is life-threatening (defined as an event in which the subject was at risk of death at the time of the event; it does not refer to an event which hypothetically might have caused death if it were more severe)
 - requires inpatient hospitalization or causes prolongation of existing hospitalization
 - results in persistent or significant disability/incapacity
 - is a congenital anomaly/birth defect (note: reports of congenital anomalies/birth defects must also be reported on the Pregnancy Supplemental Form)
 - is an important medical event (defined as a medical event(s) that may not be immediately life-threatening or result in death or hospitalization but, based upon appropriate medical and scientific judgment, may jeopardize the subject or may require intervention [e.g., medical, surgical] to prevent one of the other serious outcomes listed in the definition above.)
- Examples of such events include, but are not limited to, intensive treatment in an emergency room or at home for allergic bronchospasm; blood dyscrasias or convulsions that do not result in hospitalization.)

7.2 Collection and Reporting

Adverse events can be spontaneously reported or elicited during open-ended questioning, examination, or evaluation of a subject. (In order to prevent reporting bias, subjects should not be questioned regarding the specific occurrence of one or more Aes.)

If known, the diagnosis of the underlying illness or disorder should be recorded, rather than its individual symptoms. The following information should be captured for all Aes: onset, duration, intensity, seriousness, relationship to investigational product, and action taken. The investigator shall supply the sponsor and Ethics Committee with any additional requested information, notably for reported deaths of subjects.

Completion of supplemental CRFs may be requested for AEs and/or laboratory abnormalities that are reported/identified during the course of the study.

Following the subject's written consent to participate in the study, all SAEs must be collected, including those thought to be associated with clinical study procedures. All SAEs must be collected which occur within 30 days of discontinuation of dosing with double-blind study drug. All SAEs must be followed until resolution. In addition, the Investigator should notify BMS of any SAE which may occur after this time period which they believe to be certainly, probably or possibly related to investigational product.

Serious adverse events, whether related or unrelated to investigational product, must be recorded on the SAE page of the CRF and reported expeditiously to BMS (or designee) to comply with regulatory requirements. An SAE report should be completed for any event where doubt exists regarding its status of seriousness.

If the Investigator believes that an SAE is not related to the investigational product, but is potentially related to the conditions of the study (such as withdrawal of previous therapy, or a complication of a study procedure), the relationship should be specified in the narrative section of the SAE page of the CRF. Moreover, if an ongoing SAE

[name]

23

changes in its intensity or relationship to the investigational product, a follow-up SAE report should be sent immediately to the sponsor. As follow-up information becomes available it should be sent immediately using the same procedure used for transmitting the initial SAE report. Supporting documentation such as hospital discharge summaries and autopsy reports should be forwarded to BMS in the same manner. All SAEs should be followed to resolution or stabilization.

7.3 Overdose

An overdose is defined as the accidental or intentional ingestion of any dose of a product that is considered both excessive and medically important. All occurrences of overdose must be reported as an SAE (see Section 8.2 for reporting details.)

UNIT 8 : Statistical Considerations

8.1 Sample Size Estimation

The primary efficacy endpoint will be the time to first occurrence of confirmed ischemic stroke, hemorrhagic stroke, stroke of unspecified type or systemic embolism, regardless of whether the subject is receiving treatment at the time of the event. The primary objective is to determine if apixaban is non-inferior to warfarin for the primary efficacy endpoint.

A key aspect of developing the adequate sample size for this trial is arriving at the appropriate non-inferiority margin. Warfarin has been studied in 6 different placebo controlled randomized trials in subjects with AF. There is a meta-analysis for these studies.

The relative risk reduction of warfarin compared with placebo in these trials using a random effects model was 0.36 (95% CI 0.24-0.53), such that the inverse of the upper boundary (ie, control compared with warfarin) is 1.88 (1/0.53). To establish that at least half of the warfarin effect is preserved, the noninferiority margin is 1.88 or 1.38 (ie, the margin is the midpoint between 1.0 and 1.88 on a log scale rather than linear scale because the primary parameter estimated is the logarithm of the relative risk)

Defining a treatment effect on the log scale seems arguably more sensible statistically and mathematically for one basic reason. Suppose that the risk ratio C/P is 0.53, which amounts to a $1-0.53=0.47 = 47\%$ reduction of risk by the control relative to the placebo. But, by inversion, $P/C = 1/0.53 = 1.88$ which amounts to a 88% increase by the placebo relative to the control. The 47% decrease is not equal to the opposite of the 88% increase. This awkward difference may cause difficulty in interpretation of a treatment effect. Defining a treatment effect on the log risk ratio scale will avoid the difficulty because $\log C/P = -\log P/C$ and thus the effect of C vs. P differs from the effect of P vs. C only by sign.

Using the meta-analysis for these 6 studies is showed that the events/patient-year for warfarin is 2.38 %. So, the events/patient-year for apixaban is $1.38 * 2.38 = 3.28\%$.

It is set that the duration of the study is 2.3 years. From the literature it is known that the number of the strokes is 1.2 / 100 patient-years.

As a result the sample size for power 90% , p-value 5% and $\Delta = 3.28-2.38=0.9\%$ is

$$n \geq \left(\frac{p_1^{*(1-p_1)} + p_2^{*(1-p_2)}}{D^2} \right) * (1.96 + 1.28)^2$$

$$n \geq \left(\frac{0.0238 * (1 - 0.0238) + 0.0328 * (1 - 0.0328)}{0.009^2} \right) * (1.96 + 1.28)^2$$

$$n \geq \frac{0.023 + 0.032}{0.000081} * (1.96 + 1.28)^2$$

$$n \geq \frac{0.055}{0.000081} * 10.5$$

$$n \geq 7130$$

After the sample size estimation in each treatment, add additional 10%

Thus, the sample size is 7843 for each treatment. Overall $n=7843*2=15.686$

Determination of number of events :

15.686 subjects

So, at 2.3 years which is the duration of trial the patient years are $2,3*15.686=36.078$ patient-years

It is known as is mentioned that there are 1,2 strokes at 100 patient-year

For the study need the number of events at 36.078 patient-year. So, the number of events is $(1.2*36.078)/100=433$

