Follow-up Visits: Follow-up of subjects who discontinued study drug prior to the attainment of 433 primary efficacy events in the study should occur quarterly by a telephone call; the final follow-up visit should be in person, if at all possible, and should be performed within approximately 30 days after the attainment of 433 primary efficacy events in the study. Subjects who completed double-blind treatment with study drug should have a telephone contact approximately 30 days after the last dose of double-blind study drug. SAEs (that occurred within 30 days after the last dose of double-blind study drug) and study outcomes will be documented at all follow-up contacts.

Randomization: Eligible subjects will be randomized in a 1:1 ratio to either apixaban or warfarin titrated to a target INR range 2.0 to 3.0. Subjects who are on warfarin or another Vitamin K antagonist (VKA) prior to randomization will have their VKA discontinued prior to randomization. Each arm will contain 7,843 subjects. The randomization will be stratified by investigative site and prior warfarin/VKA status (experienced, naïve). A subject will be classified as warfarin naïve if they have not previously received warfarin or another VKA or have received \leq 30 consecutive days of treatment with warfarin or another VKA in the past. Otherwise the subject will be classified as warfarin experienced.

Duration of Study: The expected duration of the study, from first subject, first visit through the last follow-up phone contact for the last subject, is approximately 60 months.

Number of Subjects per Group: 15,686 subjects (7,843 subjects for each treatment group).

Study Population: Males and females ≥ 18 years of age with AF and one or more of the following additional risk factors for stroke: (1) age ≥ 75 years, (2) previous stroke, transient ischemic attack (TIA) or systemic embolism (SE), (3) symptomatic congestive heart failure or left ventricular dysfunction with an LVEF $\leq 40\%$, (4) diabetes mellitus, or (5) hypertension requiring pharmacological treatment.

Test Product, Dose and Mode of Administration, Duration of Treatment: Oral apixaban 5 mg or 2.5 mg tablets given BID or matching placebo for the treatment period (average of 2.3 yrs of follow-up from randomization).

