4.1 Study Design and Duration

This study is designed to evaluate the efficacy and safety of apixaban compared to warfarin (INR target range 2.0 - 3.0), a drug approved and widely employed for the prevention of stroke and systemic embolism in subjects with nonvalvular atrial fibrillation with additional risk factor(s) for stroke. The primary endpoint, a composite of stroke (ischemic, hemorrhagic, or of unspecified type) and systemic embolism will be tested using a noninferiority approach. The trial will be event driven thus the number of subjects required and length of treatment are best estimates based on event rates in similar trials. The expected duration of the study, from first subject, first visit through the last follow-up phone contact for the last subject, is approximately 60 months, but the final duration per subject will be determined by the time required to accrue 433 primary efficacy events. All subjects will be followed from randomization until the study end date.

Eligible subjects will be randomized in a 1:1 ratio to either apixaban or warfarin. Each arm will contain ~7.843 subjects (for a total of ~15.686 randomized subjects). Subjects with AF and at least one additional risk factor for stroke will be evaluated for study eligibility. Emphasis will be placed on recruiting both warfarin naïve and warfarin experienced subjects into the trial. The study will be double-blind, double-dummy, with titration based on central monitoring of INR measurements utilizing encrypted point of care (POC) devices, centralized dosing recommendations, and sham apixaban titration. Subjects will receive active apixaban tablets and placebo warfarin tablets or placebo apixaban tablets and active warfarin tablets.

INR testing frequency will occur at least every month during the treatment period, more frequently during titration and if clinically indicated. Each subject will return to have a blood sample drawn and processed in a POC device. The device will deliver an encrypted result to the Investigator who will telephone or electronically transmit the result. This facility will process the information in a blinded manner and return either a true INR value (in the case of a subject receiving warfarin) or a sham INR value (in the case of a subject receiving apixaban), along with a dosage recommendation. The final dosing decision will rest with the Investigator.

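### Section 8.1 derives N from 2.38 events per 100 patient-years but the 433-event stopping target from 1.2, so the sizing rate and the planned 2.3-year follow-up cannot both stand

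*Protocol*

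**What the plan says.** Section 8.1 first gives a warfarin rate: "Using the meta-analysis for these 6 studies is showed that the events/patient-year for warfarin is 2.38" percent. It multiplies this by the margin of 1.38 to get 3.28% for apixaban. Both annual rates are entered as proportions in a difference-in-proportions formula with a difference of 0.9%, 90% power and z-values of 1.96 and 1.28. The result is 7,130 per arm, raised by 10% to 7,843, or 15,686 in total.

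The same section then sets the follow-up, "It is set that the duration of the study is 2.3 years", and brings in a second rate, "From the literature it is known that the number of the strokes is 1.2 / 100 patient-years". The number of events is computed from that second rate: "It is known as is mentioned that there are 1,2 strokes at 100 patient-year", applied to 36,078 patient-years, gives 433.

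The 433 figure governs conduct. Section 4.1 states that "the final duration per subject will be determined by the time required to accrue 433 primary efficacy events", and sections 6.1 and 6.1.2 end the treatment and follow-up periods by it. The synopsis describes the treatment period as an "average of 2.3 yrs of follow-up from randomization".

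**The concern.** Both rates are applied to the same population and the same primary endpoint. They differ by a factor of about two (2.38/1.2 = 1.98), and nothing in the protocol explains why. One decides how many subjects are enrolled and the other decides when the trial stops.

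A reader therefore cannot tell whether the trial will deliver about 2.3 years of exposure per subject or about half of that. The difference matters for what is not fixed by the event count: major bleeding (the primary safety endpoint), all-cause death (the last step of the testing hierarchy) and fractures. The calendar timing of the interim analysis at 50% of events (section 8.4) is uncertain for the same reason.

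In addition, 433 is only an expected count. Section 8.1 does not connect it to alpha, power or the margin, although in an event-driven trial the event count determines the power of the primary test.

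**Working it through.** **Inputs (section 8.1 unless noted).** Warfarin rate 0.0238 per year; apixaban rate at the margin 0.0328; second rate 0.012; follow-up 2.3 years (an average per subject, from the synopsis); 15,686 subjects, 1:1; margin 1.38; 90% power; 5% with z = 1.96, that is, one-sided 0.025.

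**1. The protocol's own figures reproduce.**
- N: [0.0238 × 0.9762 + 0.0328 × 0.9672] / 0.009² × (1.96 + 1.28)² = 7,123 unrounded. With the printed rounding, 0.055 / 0.000081 × 10.5 = 7,130. Then 7,130 × 1.10 = 7,843 per arm.
- Events: 15,686 × 2.3 = 36,078 patient-years, and 36,078 × 0.012 = 433.

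Each calculation is right on its own inputs. The 2.3 years does not enter the formula for N.

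**2. Apply the sizing rate to the event count.**
- Both arms at 2.38: 36,078 × 0.0238 = 859 events.
- Apixaban at 3.28: the mean rate is (2.38 + 3.28)/2 = 2.83, and 36,078 × 0.0283 = 1,021 events.
- Time to the 433rd event at 2.38: 433 / 0.0238 = 18,193 patient-years, and 18,193 / 15,686 = 1.16 years of mean follow-up.
- With exponential event times instead of a flat rate, the figures are 836 events and 1.18 years.

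**3. Apply the event-count rate to the derivation of N.**
- 1.2 × 1.38 = 1.656, so the margin corresponds to 1.656 − 1.2 = 0.456% per year, about half of the 0.9% used.
- The printed formula then gives [0.012 × 0.988 + 0.01656 × 0.98344] / 0.00456² × (1.96 + 1.28)² = about 14,207 per arm before the 10%, against 7,130. This shows only that the printed derivation does not hold at 1.2. It is not the sample size that the Cox test needs.

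**4. What the planned Cox test needs (true hazard ratio 1, one-sided 0.025).**
- Events for 90% power: 4 × (1.96 + 1.2816)² / (ln 1.38)² = 42.03 / 0.1037 = 405.2, rounded up to 406.
- Power with 433 events: Φ(0.3221 × √433 / 2 − 1.96) = Φ(1.39) = 91.8%.

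**5. Which figures agree.**

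| Rate per 100 patient-years | Events at 15,686 × 2.3 years | Mean follow-up at event 433 | Subjects for 433 events at 2.3 years |
|---|---|---|---|
| 1.2 | 433 | 2.30 years | 15,688 |
| 2.38 | 859 | 1.16 years | 7,910 |

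At 1.2, N, 2.3 years and 433 fit together because 433 was computed from them. At 2.38 they do not.

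**The case against.** The strongest reply is that the primary test is unharmed. Section 4.1 makes the trial event-driven and describes subject numbers and length of treatment as best estimates. If the true rate is not 1.2, calendar time changes but the 433 events and their power do not. The protocol also sets no minimum exposure for bleeding, death or fractures, so a shorter trial breaches no stated requirement, and the halving occurs only if 2.38 is the rate in this trial. All of this stands, and it limits the point to trial length, exposure and the basis of N.

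It does not remove the contradiction. Best estimates of N and follow-up should come from one assumed rate, and here they come from two.

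A reader might infer more than the documents support:
- **That N must roughly double.** The 14,207 comes from an absolute-difference formula, whereas the analysis is a Cox test of a ratio.
- **That the 10% addition leaves too few events.** Section 8.1 does not say that these subjects contribute no follow-up. Subjects who stop study drug are followed on, and the trial does not stop at a fixed 2.3 years.
- **That 1.2 covers a narrower endpoint because it is worded as strokes.** Section 8.1 uses strokes and events interchangeably and does not define the endpoint behind 2.38, so a real mismatch cannot be shown.

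**Conclusion.** Section 8.1 is wrong as written. The sizing rate of 2.38, the N of 15,686, the 2.3-year follow-up and the 433 events cannot all hold. At the sizing rate, the stated N and follow-up would produce about twice the target (859, or 1,021 with apixaban at 3.28), and the trial would stop at about 1.16 years of mean follow-up. At 1.2, the difference behind the printed N is about half of what was assumed.

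It would be natural to infer that the trial is underpowered. It is not: 433 events give about 91.8% power at the 1.38 margin, above the stated 90%. That adequacy is a coincidence of the derivation, since 433 was not obtained from the test.

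The event counts and follow-up times assume a constant rate and full follow-up. The power figures assume a true hazard ratio of 1, equal allocation and one-sided 0.025. Which rate is correct cannot be settled from the protocol, because its sources for both are not at hand.

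**What to change.** 1. Choose one pooled annual rate for stroke or systemic embolism, justify it in section 8.1, and use it throughout.
2. Justify the event target from the Cox log-hazard-ratio test: 406 events give 90% power at 1.38. The target of 433 can be kept, with its power of 91.8% and the assumptions behind it stated.
3. Replace the difference-in-proportions derivation of N with one from the event target, the chosen rate and the intended follow-up: subjects = events / (rate × mean follow-up), with any allowance for loss stated separately. At 1.2 and 2.3 years, 433 events need about 15,688 subjects, in line with the present N. At 2.38, they need either about 7,910 subjects for 2.3 years or the present N for about 1.16 years. If the shorter follow-up is chosen, the protocol should say whether that exposure is enough for the safety endpoints.
4. Restate patient-years, expected mean follow-up and overall duration to match in sections 8.1 and 4.1 and in the synopsis.

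The cost is a rewrite of section 8.1 and the matching lines in 4.1 and the synopsis. No patients need be added, and the 433-event rule can stay.
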